4.2 Site Registration

This study is supported by the NCI Cancer Trials Support Unit (CTSU).

Each investigator or group of investigators at a clinical site must obtain IRB approval for this protocol and submit IRB approval and supporting documentation to the CTSU Regulatory Office before they can be approved to enroll patients. Assignment of site registration status in the CTSU Regulatory Support System (RSS) uses extensive data to make a determination of whether a site has fulfilled all regulatory criteria including but not limited to the following:

- An active Federal Wide Assurance (FWA) number
- An active roster affiliation with the Lead Network or a participating organization
- A valid IRB approval
- Compliance with all protocol specific requirements.

In addition, the site-protocol Principal Investigator (PI) must meet the following criteria:

- Active registration status
- The IRB number of the site IRB of record listed on their Form FDA 1572
- An active status on a participating roster at the registering site

Sites participating on the NCI CIRB initiative that are approved by the CIRB for this study are

not required to submit IRB approval documentation to the CTSU Regulatory Office. For sites using the CIRB, IRB approval information is received from the CIRB and applied to the RSS in an automated process. Signatory Institutions must submit a Study Specific Worksheet for Local Context (SSW) to the CIRB via IRBManager to indicate their intent to open the study locally. The CIRB's approval of the SSW is then communicated to the CTSU Regulatory Office. In order for the SSW approval to be processed, the Signatory Institution must inform the CTSU which CIRB-approved institutions aligned with the Signatory Institution are participating in the study.

All ETCTN sites are part of an LAO (Lead Academic Organization), which must use their own funding to participate in any ETCTN trial. Other comprehensive cancer centers can participate in ETCTN trials via the EDDOP program and are awarded funding that can be used to facilitate their participation in NCI-CTEP trials. (<https://ctep.cancer.gov/initiativesprograms/eddop.htm>)

4.2.1 Downloading Regulatory Documents

Site registration forms may be downloaded from the 9875 protocol page located on the CTSU Web site. Permission to view and download this protocol is restricted and is based on person and site roster data housed in the CTSU RSS. To participate, Investigators and Associates must be associated with the Corresponding or Participating protocol organization in the RSS.

- Go to <https://www.ctsuo.org> and log in using your CTEP IAM username and password.
- Click on the Protocols tab in the upper left of your screen.
- Either enter the protocol # in the search field at the top of the protocol tree, or
- Click on the "By Lead Organization" folder to expand, then select LAO-MA036, and protocol #9875.
- Click on LPO Documents, select the Site Registration documents link, and download and complete the forms provided. (Note: For sites under the CIRB initiative, IRB data will load to RSS as described above.)

4.2.2 Requirements For 9875 Site Registration:

- IRB approval (For sites not participating via the NCI CIRB; local IRB documentation, an IRB-signed CTSU IRB Certification Form, Protocol of Human Subjects Assurance Identification/IRB Certification/Declaration of Exemption Form, or combination is accepted)

4.2.4 Checking Site Registration Status

You can verify your site registration status on the members' section of the CTSU website.

- Go to <https://www.ctsu.org> and log in using your CTEP IAM username and password.
- Click on the Regulatory tab at the top of your screen.
- Click on the Site Registration subtab.
- Enter your 5-character CTEP Institution Code and click on Go.

Note: The status given only reflects compliance with IRB documentation and institutional compliance with protocol-specific requirements as outlined by the Lead Network. It does not reflect compliance with protocol requirements for individuals participating on the protocol or the enrolling investigator's status with the NCI or their affiliated networks.

4.3 **Patient Registration**

4.3.1 OPEN / IWRS

Study-wide, new enrollment is permanently closed, as of October 2019. Patient enrollment will be facilitated using the Oncology Patient Enrollment Network (OPEN). OPEN is a web-based registration system available to users on a 24/7 basis. It is integrated with the CTSU Enterprise System for regulatory and roster data interchange and with the Theradex Interactive Web Response System (IWRS) for retrieval of patient registration/randomization assignment. Patient enrollment data entered by Registrars in OPEN / IWRS will automatically transfer to the NCI's clinical data management system, Medidata Rave.

The OPEN system will provide the site with a printable confirmation of registration and treatment information. Please print this confirmation for your records.

4.3.2 OPEN/IWRS User Requirements

OPEN/IWRS users must meet the following requirements:

- Have a valid CTEP-IAM account (*i.e.*, CTEP username and password).

- To enroll patients: Be on an ETCTN Corresponding or Participating Organization roster with the role of Registrar. Registrars must hold a minimum of an AP registration type.
- Have regulatory approval for the conduct of the study at their site.

Prior to accessing OPEN/IWRS, site staff should verify the following:

- All eligibility criteria have been met within the protocol stated timeframes. If applicable, all patients have signed an appropriate consent form and HIPAA authorization form.

4.4 General Guidelines

Following registration, patients should begin protocol treatment within 7 days. Issues that would cause treatment delays should be discussed with the Principal Investigator. If a patient does not receive protocol therapy following registration, the patient's registration on the study may be canceled. The Study Coordinator should be notified of cancellations as soon as possible.

Except in very unusual circumstances, each participating institution will order DCTD-supplied agents directly from CTEP. Agents may be ordered by a participating site only after the initial IRB approval for the site has been forwarded by the Coordinating Center to the CTEP PIO ([contact]) except for Group studies.

5. TREATMENT PLAN

5.1 Agent Administration

Treatment will be administered on an outpatient basis. Reported adverse events and potential risks are described in Section 7. Appropriate dose modifications are described in Section 6. No investigational or commercial agents or therapies other than those described below may be administered with the intent to treat the patient's malignancy.

Regimen Description					
Agent	Premedications Precautions	Dose	Route	Schedule	Cycle Length
AT13387 (onalespib)	No premedications are required	160mg/m ² in 250 cc 5% dextrose or 0.9% NS	IV over 1 hour	Days 1, 2, 8, 9, 15 and 16	28 days (4 weeks)

Patients will be dosed at 160mg/m²/dose on days 1, 2, days 8, 9, and days 15, 16 of a 4 week cycle. There will be a response assessment by PET/CT and CT scans every 2 cycles. If the CT portion of the PET/CT is of diagnostic quality, then an additional CT scan is not necessary. However, if CT portion of the PET/CT is a low-resolution CT, then a separate CT scan is necessary.

Treatment can be moved up or delayed to accommodate holidays, inclement weather, or other reasons for clinic closures. Patients can continue on treatment as long as they are responding and tolerating treatment. However, all patients will have to come off this study treatment by May 31, 2020, as the study treatment will no longer be available.

5.1.1 AT13387 (onalespib)

The study drug AT13387 (onalespib) will be administered by intravenous infusion via peripheral or central venous access at a dose of 160mg/m² (using actual body weight from cycle 1 day 1 to calculate body surface area) over 1 hour. The dosing frequency will be on days 1, 2, 8, 9, 15, and 16 of every 4 week cycle. AT13387 (onalespib) will be provided by CTEP.

On the first day of treatment each week (days 1, 8, and 15), patients must meet the following pre-treatment criteria: ANC \geq 1000/mcL, platelet count $>$ 75,000/mcL (or $>$ 30,000/mcL if due to disease), potassium and magnesium above the institutional lower limit of normal (repletion is allowed).

Astex has recommended that vital signs (temperature, heart rate, blood pressure, oxygen saturations) be performed pre-AT13387 (onalespib) infusion. Additional vital signs will be performed during the course of infusion as clinically indicated. No extended post-administration monitoring will be required, except as indicated in the protocol for research-related assays.

5.1.2 Other Modalities or Procedures

N/A

5.2 General Concomitant Medication and Supportive Care Guidelines

All patients receiving treatment with AT13387 (onalespib) may receive antiemetics and anti-motility agents for symptomatic management while on treatment. Both antiemetics and anti-motility agents may be given to alleviate expected drug-related toxicity on an as required basis and gastrointestinal toxicity should not be considered to be dose limiting in the absence of maximal supportive therapy. Patients receiving treatment with a bisphosphonate are not excluded from participating in the trial and bisphosphonate therapy may be initiated while on trial provided the patient does not have disease progression according to RECIST criteria.

5.2.1 Growth factors

The use of white blood cell growth factors (G-CSF) is acceptable for patients who experience grade 4 neutropenia or have a history of febrile neutropenia. For these acceptable circumstances, growth factors can be administered both at the time of the

event and preventively in subsequent cycles. Growth factors should *not* be administered to allow for patient eligibility at screening. Growth factors should *not* be administered on the same day as onalespib; wait 24 hours after an administering onalespib to administer growth factors.

5.2.2 Transfusions

Symptomatic anemia should be treated with red blood cell transfusion and is recommended if the hemoglobin falls below 8 g/dL. The initiation of erythropoietic therapy for the management of chemotherapy-induced anemia follows the American Society of Hematology/ASCO clinical practice guidelines (WWW.ASCO.ORG).

Thrombocytopenia will be treated conservatively. In the absence of bleeding, or a necessary invasive procedure, platelet transfusions should be given for a platelet count $\leq 10 \times 10^9/L$. If invasive procedure(s) is (are) planned, or the patient develops bleeding, platelet transfusions should be administered in accordance with the standard of practice, usually maintaining a platelet count above $50 \times 10^9/L$.

5.2.3 Electrolyte repletion

Oral and IV potassium and magnesium electrolyte repletion is allowed to meet both study eligibility and treatment criteria.

5.2.4 Antiemetics

Antiemetics will not be administered routinely prior to receiving AT13387 (onalespib). However, if a patient develops nausea/vomiting, anti-emetics such as but not limited to prochlorperazine, metochlopramide, or aprepitant may be given. 5-HT₃ antagonists like ondansetron are not allowed given their prolonging effecting on the QTc interval. In addition, if a patient develops nausea and/or vomiting at any dose level that is Grade 2 or greater, anti-emetics may be instituted prophylactically at the discretion of the investigator. Nausea and vomiting will be considered refractory if it does not resolve to \leq Grade 1 with treatment with combination antiemetics within 48 hours.

5.2.5 Anti-motility agents

If diarrhea develops and does not have an identifiable cause other than AT13387 (onalespib) administration, anti-motility agents will be administered. Diarrhea will be considered refractory if it does not resolve within 48 hours to \leq Grade 1 with administration of anti-motility agent(s). If the patient develops blood or mucous in the stool, dehydration, or hemodynamic instability, or fever along with the diarrhea, anti-motility agents may be discontinued at the discretion of the Principal Investigator and the patient will be treated with intravenous fluids and antibiotics as medically indicated.

5.2.6 Antibiotics

Prophylactic antibiotics are not required on this trial.

5.2.7 Pre-medications

No premedication with acetaminophen, corticosteroids, or antihistamines will be routinely administered.

Local infusion-related irritation and systemic infusion reactions may occur during or shortly after the administration of AT13387 (onalespib). The local infusion adverse events are formulation-related (pH of current formulation is 5.0). Systemic adverse events (e.g.; flushing, itching, rigors, chills, nausea, tachycardia/bradycardia, dizziness) are reversible. If that occurs, slow the infusion rate and/or hydrate. If participants experience an infusion reaction they may subsequently receive acetaminophen (650mg orally), diphenhydramine (25-50mg IV), hydrocortisone (25-100mg IV), +/- famotidien (20mg IV) or equivalent as pre-medications per institutional standard of practice.

5.2.8 Hydration

No pre-hydration or hydration is required with this regimen.

5.2.9 Tumor lysis prevention and management

Participants with bulky disease and/or circulating disease $\geq 15,000$ circulating malignant cells/ mm³ may receive allopurinol 300mg orally daily for 7-10 days starting with the first dose of AT13387 (onalespib). Patients deemed at risk for tumor lysis syndrome (TLS) should have their labs monitored per standard practice. The management of established TLs should also follow standard practice.

5.2.10 Hyperglycemia

AT13387 (onalespib) is known to cause hyperglycemia in patients. Patients with pre-existing diabetes will be asked to keep a log of their fasting and post-prandial blood glucose measurements and adjustments to their diabetes medications will be adjusted accordingly. Referral to an endocrinologist will be made in cases with blood glucose management is challenging.

5.2.11 Potential drug-drug interactions

The potential for AT13387 (onalespib) to inhibit cytochromes P450 (CYP) 1A2, 3A4, 2D6, 2C9, and 2C19 was assessed, and results indicate a low potential for inhibition ($IC_{50} > 10$ mM), suggesting a low potential for clinically significant drug-drug interactions mediated by these enzymes. Because the lists of these agents are constantly changing, it is important to regularly consult a frequently-updated list such as <http://medicine.iupui.edu/clinpharm/ddis/>; medical reference texts such as the Physicians' Desk Reference may also provide this information. As part of the enrollment/informed consent procedures, the patient will be counseled on the risk of interactions with other agents, and what to do if new medications need to be prescribed or if the patient is considering a new over-the-counter medicine or herbal product. Appendix B presents guidelines for identifying medications/substances that could potentially interact with the study agent(s), as well as a Patient Drug Handout Information and Wallet Card that will be provided to each patient.

AT13387 (onalespib) is a substrate of UGT with a relatively low affinity to inhibit UGT1A1, -1A3 and -1A9. Pre-clinical studies suggest that AT13387 (onalespib) is a substrate of P-gp; thus, avoid St. John's wort, rifampin, etc. AT13387 (onalespib) is also a

moderate inhibitor of BCRP and P-gp and a strong inhibitor of MATE1/2-K; thus, use caution with concomitant drugs that are substrates of these enzymes.

5.2.12 QTc prolonging drugs

Every attempt will be made to avoid medications that have been associated with QT interval prolongation or Torsades de Pointes (see Appendix B). Antiemetics and diphenhydramine will be permitted on study with the exception of 5-HT₃ antagonists like ondansetron. Patients who are stable on antidepressants known to prolong QTc will be permitted to continue on their medication at the discretion of the Principal Investigator, provided the QTc at enrollment meets eligibility criteria.

5.3 Duration of Therapy

In the absence of treatment delays due to adverse event(s), treatment may continue until one of the following criteria applies or until May 31, 2020. All patients must be off this study treatment by May 31, 2020, as the study treatment will no longer be available.

- Disease progression,
- Intercurrent illness that prevents further administration of treatment,
- Unacceptable adverse event(s),
- Patient decides to withdraw from the study, or
- General or specific changes in the patient's condition render the patient unacceptable for further treatment in the judgment of the investigator.

5.4 Duration of Follow Up

Patients who discontinue treatment for reasons other than disease progression will be followed with CT scans at 6 and 12 months or until disease progression or next therapy for PFS and DOR endpoints. Follow-up after treatment discontinuation for progression, or after documented progression following discontinuation of therapy for reasons other than progression initially, will be by phone every 6 months for up to 1 year after the discontinuation of treatment for OS endpoints. Patients removed from study for unacceptable adverse event(s) will be followed until resolution or stabilization of the adverse event.

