10. STUDY CALENDAR

Baseline evaluations are to be conducted within 2 weeks prior to start of protocol therapy. Scans and x-rays, including LVEF evaluation, must be done ≤ 6 weeks prior to the start of therapy and bone marrow biopsy must be done ≤ 6 weeks prior to the start of therapy. In the event that the patient's condition is deteriorating, laboratory evaluations should be repeated within 48 hours prior to initiation of the next cycle of therapy.

		Cycle 1								Cycle 2+		
	Pre-Study ^a	D 1	D 2	D 8	D 9	D 15	D 16	D 17	D 18	D 1,8,15	D 2,9,16	Off Treatment ⁱ
AT13387 (onalespib)		A	A	A	A	A	A			A	A	
Informed consent	X											
Demographics	X											
Medical history	X											
Detailed eye exam ^b	X											
Concurrent meds	X	X-----X										
Physical exam	X	X		X		X				X		X
Vital signs	X	X	X	X	X	X	X			X	X	X
Height	X											
Weight	X	X	X	X	X	X	X			X	X	X
Performance status	X	X		X		X				X		X
CBC w/diff, plts	X	X		X		X		X		X		X
Serum chemistry ^c	X	X		X		X		X		X		X
EKG ^d	X	X		X		X				X ^d		X
LVEF evaluation (TTE or MUGA)	X											
Adverse event evaluation ^e		X-----X										X
Bone marrow biopsy	X											X ^f
Blood sample for germline sequencing ^g	X											
Radiologic evaluation												
FDG-PET/CT scans	X									FDG-PET/CT should be performed every 8 weeks +/- 3 days		X
CT chest/abdomen/pelvis	X									CT scans should be performed every 8 weeks +/- 3 days		X ⁱ
B-HCG ^h	X											
Tumor biopsy ^k	X							X				X

A: AT13387 (onalespib): 160mg/m²/dose as assigned
a: All screening must take place within 2 weeks of the start of therapy, except for scans, which must occur within 6 weeks, and the screening bone marrow biopsy, which must occur within 6 weeks, prior to the start of therapy.
b: All patients will have a detailed eye exam by an ophthalmologist during screening to be used as a baseline eye exam for comparison, should ocular toxicity later develop. There are no protocol-specific tests required for this eye exam. If patients develop eye symptoms during treatment, an additional eye examination may be conducted at the investigator's discretion. See appendix I for an example of an eye exam work-up. Using this eye exam form is *not* required.
c: Albumin, alkaline phosphatase, total bilirubin, bicarbonate, BUN, calcium, chloride, creatinine, glucose, LDH, phosphorus, potassium, magnesium, total protein, SGOT [AST], SGPT [ALT], sodium, uric acid.

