d: Cycle 2 and on, electrocardiograms (EKGs) will be done on day 1 of each cycle. EKGs should be done per standard of care at the treating institution. EKGs are not required to be in triplicate, but if there is an issue with a QTc value on the single EKG, an average QTc is acceptable on three triplicate EKGs if it makes a patient eligible for treatment.
e: Adverse event and concomitant medication evaluation will be assessed at each visit by the clinical trial personnel.
f: If bone marrow biopsy is negative at screening, it does not need to be repeated. If the bone marrow biopsy is involved at baseline, it must be repeated in order to confirm a complete response (CR).
g: To be collected in 1 x 4 mL purple top EDTA tube. However, a minimum of 1 mL of blood is needed so any tube size that meets this 1 mL minimum is acceptable. This can be shipped along with the frozen tissue.
h: Serum pregnancy test (women of childbearing potential).
i: Off-treatment evaluation. Patients who come off treatment for progression will have telephone follow-up every 6 months for up to 1 year

- | |
|--|
| 
for OS endpoints. Patients who come off treatment for reasons other than progression will have CT scans (see below) at 6 and 12 months, or until the time of progression or next therapy, for PFS and DOR endpoints.
 
j: CT scans will be repeated at 6 and 12 months, or until the time of progression, for patients who come off study for reasons other than disease progression.
 
k: Biopsy or sample of most accessible tissue, which may be bone marrow, body fluid, lymph node, or other tumor site. The sample should be from the same tumor source (ie body fluid, bone marrow, lymph node, or other tumor site) at each timepoint. This is distinct from the bone marrow biopsy required at screening for lymphoma staging. However, if the bone marrow is involved at screening, this can be used as the site of tumor biopsy for patients during pre-treatment, cycle 1 and at the time of progression. Biopsies during cycle 1 should optimally be done on day 17, but can be done between days 17-22.
 |
|--|

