11. MEASUREMENT OF EFFECT

11.1 Antitumor Effect

All patients will have a baseline PET/CT scan within 6 weeks prior to the start of therapy. For the purposes of this study, patients should be re-evaluated for response by PET/CT scans every 8 weeks. In addition, a bone marrow aspirate and biopsy are required within 6 weeks before the 1st treatment for all patients. If the initial marrow shows involvement, repeat marrow is required to confirm a CR. If the initial marrow is negative, further bone marrow biopsy is not required. The marrow should be sent for aspirate, core pathology, flow cytometry, and cytogenetics.

Response and progression will be evaluated in this study using the International Harmonization Project for lymphoma criteria.¹⁰⁴

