13.4 Analysis of Secondary Endpoints

Secondary endpoints will be analyzed at the same time as the primary endpoint and assessed for each cohort separately and overall. Due to the small sample size in each cohort and all patients combined, secondary endpoints will be descriptive unless otherwise noted. All eligible patients who receive at least one dose of treatment will be included in efficacy endpoints, and all patients regardless of eligibility who receive at least one dose of treatment will be included in toxicity assessments.

Patients receiving any treatment regardless of eligibility or study completion will be assessed for toxicity from the time of their first treatment. At each toxicity evaluation, patients with unacceptable toxicities will be removed from study but remain in safety evaluations. Toxicities will be summarized with counts and proportions within each cohort and overall.

Time-to-event endpoints of progression-free and overall survival (PFS and OS, resp.) will be characterized using the Kaplan-Meier method. OS is defined from the date of study entry until the date of death by any cause. PFS will be measured from the date of study entry until documentation of first progression or death from any cause. Median follow-up time will be assessed using the reverse Kaplan-Meier method.

Duration of response (DOR) is defined as the time from first objective response (PR or CR) until the first date of documented progression using [the response criteria] or death due to any cause. For patient who remain alive without progression, the DOR will be censored on the date of their last response assessment. Patients who begin a subsequent therapy without prior documented progression will be censored at the last response assessment prior to initiation of non-protocol therapy. DOR will be evaluated only in patients who respond with either a PR or CR while on study.

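### Progressions found after a non-progression stop are dated up to 6 months late, which biases Kaplan-Meier PFS upward; an interval-censored sensitivity analysis would show by how much

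*Combined protocol and SAP*

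**What the plan says.** While on treatment, "patients should be re-evaluated for response by PET/CT scans every 8 weeks" (Section 11.1), and the Section 10 calendar likewise states that "CT scans should be performed every 8 weeks +/- 3 days".

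After a stop for any reason other than progression, Section 5.4 says that patients "will be followed with CT scans at 6 and 12 months or until disease progression or next therapy for PFS and DOR endpoints". The calendar footnote agrees: "Patients who come off treatment for reasons other than progression will have CT scans (see below) at 6 and 12 months". The calendar also marks imaging at the off-treatment evaluation. Neither place says what the 6 and 12 months are counted from.

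Section 13.4 then states: "Time-to-event endpoints of progression-free and overall survival (PFS and OS, resp.) will be characterized using the Kaplan-Meier method". On the event date it says: "PFS will be measured from the date of study entry until documentation of first progression or death from any cause". DOR also ends at the first documented progression or death. Section 13.4 names no estimator for DOR. It gives censoring rules for DOR but none for PFS, and it has no interval-censored method, no rule for long assessment gaps and no sensitivity analysis. These endpoints are secondary and descriptive.

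Section 5.3 adds a fixed end date: "All patients must be off this study treatment by May 31, 2020, as the study treatment will no longer be available".

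**The concern.** Kaplan-Meier treats the documentation date as the event date. The resulting error is small and roughly even when everyone is scanned every 8 weeks. Here the gap between scans roughly triples when a patient stops without progression, so the error depends on why and when treatment ended. It runs in one direction only: a late date can lengthen PFS or DOR but never shorten it.

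Stopping without progression is foreseeable. Section 5.3 lists intercurrent illness, adverse events, withdrawal and investigator judgment, and Section 6 takes patients off therapy for long delays or repeated dose reductions. Section 2.2.1.2 reports grade 3/4 events in 49.1% of patients given the drug. Because these endpoints carry no test, the curve and the median are all that a reader takes from them into planning the randomized trial that Section 2.3.3 anticipates.

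**Working it through.** The documents give no figure for PFS, DOR or detection delay, so there is none to reproduce on this point. The response-rate design does reproduce: early stopping 59.9% and 5.63%, type I error 6.86% and power 88.2%, against the stated 60%, 5.6%, 6.9% and 88%. It uses no progression dates.

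**Delay per progression.** Inputs: 8 weeks = 56 days = 1.84 months (Sections 10 and 11.1); off-treatment gaps of 6 months (Section 5.4), taken here as counted from discontinuation. For a constant progression rate λ = ln 2 / median and scan gap L, the mean delay of a scan-detected progression is L / (1 − e^(−λL)) − 1/λ. For a 3-month median after stopping, with L = 6: 6 / 0.75 − 4.33 = 3.67 months.

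| Assumed median after stopping (months) | Mean delay, 6-month gaps | Mean delay, 8-week gaps |
|---|---|---|
| 1 | 4.65 | 1.11 |
| 3 | 3.67 | 0.98 |
| 6 | 3.34 | 0.95 |
| 12 | 3.17 | 0.94 |

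The longest possible delay is 6 months off treatment and 1.84 months on treatment.

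**Effect on the PFS curve.** Assumptions, none of them from the documents: exponential PFS with median 4 months, so S(t) = 2^(−t/4); 22% of the cohort stop progression-free at one of the first three 8-week scans, in proportion to those still progression-free at each; progression is found by scheduled scan only.

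- S(1.84) = 0.727, S(3.68) = 0.529, S(5.52) = 0.384, S(7.36) = 0.279, S(6) = 0.354.
- Shares stopping: 0.22 × (0.727, 0.529, 0.384) / 1.640 = 0.0975, 0.0709, 0.0516.
- Their first off-treatment scans fall at 7.84, 9.68 and 11.52 months.

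At the fourth 8-week scan (7.36 months) none of the stopped patients has been rescanned. The excess is 0.0975 × (1 − 0.384) + 0.0709 × (1 − 0.529) + 0.0516 × (1 − 0.727) = 0.0600 + 0.0334 + 0.0141, or 10.8 points: 38.7% against a true 27.9%.

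For later times, the share still on treatment and progression-free at 7.36 months is 0.279 − (0.0975 × 0.384 + 0.0709 × 0.529 + 0.0516 × 0.727) = 0.167. It falls by the factor 0.727 at each further 8-week scan. Each stopped group falls by the factor 0.354 at its own 6-month scan.

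| Month | Kaplan-Meier as planned | If 8-weekly scans had continued | True | Excess over true |
|---|---|---|---|---|
| 7.4 (fourth scan) | 38.7% | 27.9% | 27.9% | 10.8 |
| 7.9 | 0.167 + 0.0345 + 0.0709 + 0.0516 = 32.4% | 27.9% | 25.4% | 6.9 |
| 9.7 | 0.121 + 0.0345 + 0.0251 + 0.0516 = 23.2% | 20.3% | 18.6% | 4.6 |
| 11.6 | 0.0882 + 0.0345 + 0.0251 + 0.0182 = 16.6% | 14.8% | 13.4% | 3.2 |

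Simulation gave 39.0%, 32.0%, 22.9% and 16.7% at these times, in agreement. Part of the later excess (1.4 to 2.5 points) is the ordinary 8-week step and would remain under dense scanning.

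**Sensitivity.**
- Half of off-treatment progressions documented when they occur: the 7.4-month excess halves to about 5.4 points.
- 10% stopped instead of 22%: 10.8 × 10/22 = 4.9 points at 7.4 months.
- The Kaplan-Meier median is 5.52 months under both schedules in the 4-month case. With a true median of 6 months and 26% stopped, it moves from 7.36 to 7.84 months.

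**Does interval censoring recover the truth?** In simulation the Turnbull estimate at 7.4 months was 27.6% to 28.0% against 27.9%. With 28% stopped and n = 20, Kaplan-Meier averaged 42.0% (SD 11.4 points) and Turnbull 28.2% (SD 12.0). With n = 10 the averages were 42.7% and 31.4%.

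**The case against.** The strongest reply is that 7.4 months is an unfavourable place to read the curve. It falls just before the first off-treatment scan, when the on-treatment error is zero and no off-treatment progression has yet been found. The gap narrows quickly after that and the median barely moves. This stands, and it is why the size is given as a range over time.

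Four stronger readings are tempting, and the documents do not support them.

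- *Every off-treatment progression is dated at the end of the gap.* Deaths are dated exactly, nothing bars unscheduled imaging, a responder who starts new therapy is censored for DOR at the last assessment, and a patient who withdraws from the study (Section 5.5) has no later scan. Only scan-detected progressions are affected.
- *The 31 May 2020 stop drives the bias.* ALCL and MCL closed to enrolment in February 2019, so anyone forced off there was about 15 months or more from entry. Under assumed medians of 4 and 6 months, 2^(−15/4) = 7% and 2^(−15/6) = 18% would still be progression-free. Only late DLBCL entrants (closed October 2019) could be forced off at about 7 months. The group may be small and would mostly affect the late tail.
- *DOR is overstated by a known amount.* The direction is likely, but no DOR figure has been derived, and response onset is itself known only to within a scan interval.
- *Kaplan-Meier must be replaced as the main analysis.* For descriptive endpoints in cohorts of 10 to 20, that is a preference. The sampling error of a 28% estimate is √(0.28 × 0.72 / n), or 10 points at n = 20 and 14 at n = 10, comparable to the largest bias shown.

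Sampling error does not excuse the bias, however. It is shown by a confidence interval, whereas the bias is not shown anywhere.

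**Conclusion.** The concern holds as a cheap improvement. Followed as written, the plan dates scan-detected off-treatment progressions up to 6 months late (mean about 3 to 4.7 months, against about 1 month under 8-weekly scans). This biases PFS upward and probably DOR as well. Under an assumed 4-month median with 22% stopping early, the excess over true PFS is about 11 points at 7.4 months and about 3 to 7 points from 8 to 12 months. With half of those progressions documented promptly, it is about 5 points at 7.4 months.

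These sizes rest on an exponential PFS curve, assumed stopping shares, and 6 and 12 months counted from discontinuation. The true share stopping progression-free is not in the documents. The response-rate rules and their error rates do not change.

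**What to change.** In Section 13.4, keep Kaplan-Meier on documented dates and add a pre-specified interval-censored nonparametric (Turnbull) sensitivity analysis of PFS, and of DOR where the number of responders allows. Place each scan-detected progression between the last progression-free scan and the first scan showing progression, and keep deaths at their exact dates. State what the 6 and 12 months are counted from. Report for each cohort how many patients moved to the 6- and 12-month schedule, and how many of those did so because supply ended.

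The cost is a few lines of SAP text and one extra analysis on scan dates already collected, with no additional scans. The sensitivity estimates will be slightly less favourable and less smooth than the Kaplan-Meier curve.
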